#### **2) PSA Progression**

PSA progression is defined as  $\geq 25\%$  increase and  $\geq 2$  ng/mL increase above the nadir or baseline value for patients who had a PSA decrease on treatment, which is confirmed by a second value 3 or more weeks later.

For patients without a decrease on treatment, PSA progression is defined as  $\geq 25\%$  increase and an absolute increase of  $\geq 2$  ng/mL after 12 weeks.

PSA progressions must be confirmed at the next study visit 4 weeks later. PSA will be collected at screening and on Day 1 of each treatment cycle.

*CONFIDENTIAL*

Study Drug: AC176

Sponsor/Development Innovations Study Number: AC176-001/GU 207

Final Protocol: 10 July 2023 Version 4.0

## Appendix C: PCWG3 Criteria (continued)

### 3) Symptomatic Progression

Symptomatic progression is defined as evidence of unequivocal symptomatic or clinical progression defined by at least 1 of the following:

- A marked escalation in cancer-related pain that is assessed by the Investigator to indicate the need for other systemic therapy or palliative radiotherapy. Ignore early changes ( $\leq 12$  weeks) in pain or health-related quality of life in absence of compelling evidence of disease progression. Confirm progression of pain or health-related quality of life  $\geq 3$  weeks later
- An immediate need for initiation of new anticancer treatment or surgical or radiological intervention for complications due to tumor progression
- A marked deterioration in ECOG performance status to Grade 3 or higher or
- It is felt to be in the best interest of the patient to come off study due to clinical progression

**Reference:** Scher et al. 2016

## **Appendix D: Guidelines for Fertile Male Patients**

### **Acceptable Contraception Methods:**

Fertile male subjects, defined as all males physiologically capable of conceiving offspring, with female partners of childbearing potential must use condoms plus spermicidal agent during the study treatment period and for 90 days after the last dose of the study drug, and should not father a child during this period.

Male subjects must also refrain from donating sperm during their participation in the study and for 90 days after the last dose of the study drug.

### **Pregnancies**

Pregnancy outcomes must be collected for the female partners of any males who took study drug in this study. Consent to report information regarding these pregnancy outcomes should be obtained from the mother.

*CONFIDENTIAL*

Study Drug: AC176

Final Protocol: 10 July 2023 Version 4.0

Sponsor/Development Innovations Study Number: AC176-001/GU 207

## Appendix E: New York Heart Association Classification of Cardiac Disease

The following table presents the New York Heart Association classification of cardiac disease.

Class	Functional Capacity	Objective Assessment
I	Subjects with cardiac disease but without resulting limitations of physical activity. Ordinary physical activity does not cause undue fatigue, palpitation, dyspnea, or anginal pain.	No objective evidence of cardiovascular disease.
II	Subjects with cardiac disease resulting in slight limitation of physical activity. They are comfortable at rest. Ordinary physical activity results in fatigue, palpitation, dyspnea, or anginal pain.	Objective evidence of minimal cardiovascular disease.
III	Subjects with cardiac disease resulting in marked limitation of physical activity. They are comfortable at rest. Less than ordinary activity causes fatigue, palpitation, dyspnea, or anginal pain.	Objective evidence of moderately severe cardiovascular disease.
IV	Subjects with cardiac disease resulting in inability to carry on any physical activity without discomfort. Symptoms of heart failure or the anginal syndrome may be present even at rest. If any physical activity is undertaken, discomfort is increased.	Objective evidence of severe cardiovascular disease.

Source: The Criteria Committee of New York Heart Association. Nomenclature and Criteria for Diagnosis of Diseases of the Heart and Great Vessels. 9th Ed. Boston, MA: Little, Brown & Co; 1994:253-256.

## Appendix F: Hy's Law

Reference: FDA Guidance for Industry (issued July 2009) "Drug-induced liver injury: Premarketing clinical evaluation"

### Introduction

This Appendix describes the process to be followed in order to identify and appropriately report cases of Hy's Law (HL). It is not intended to be a comprehensive guide to the management of elevated liver biochemistries. Specific guidance on managing liver abnormalities can be found in Section 6.2.1 of the clinical study protocol.

During the course of the study the Investigator will remain vigilant for increases in liver biochemistry. The Investigator is responsible for determining whether a subject meets potential Hy's Law (PHL) criteria at any point during the study.

The Investigator participates, together with Accutar Biotechnology, Inc. clinical project representatives, in review and assessment of cases meeting PHL criteria to agree whether HL criteria are met. Hy's Law criteria are met if there is no alternative explanation for the elevations in liver biochemistry other than drug-induced liver injury (DILI) caused by the investigational medicinal product.

The Investigator is responsible for recording data pertaining to PHL/HL cases and for reporting adverse events (AEs) and serious adverse events (SAEs) according to the outcome of the review and assessment in line with standard safety reporting processes.

### Definitions

#### Potential Hy's Law (PHL)

Aspartate aminotransferase (AST) or alanine aminotransferase (ALT)  $\geq 3 \times$  the upper limit of normal (ULN) together with total bilirubin (TBL)  $\geq 2 \times$  ULN at any point during the study following the start of study medication, irrespective of an increase in alkaline phosphatase (ALP).

#### Hy's Law (HL)

Aspartate aminotransferase or ALT  $\geq 3 \times$  ULN together with TBL  $\geq 2 \times$  ULN, where no other reason other than the investigational product can be found to explain the combination of increases, e.g., elevated ALP indicating cholestasis, viral hepatitis, another drug.

For PHL and HL the elevation in transaminases must precede or be coincident with (i.e., on the same day) the elevation in TBL, but there is no specified time frame within which the elevations in transaminases and TBL must occur.

### Identification of potential Hy's Law cases

In order to identify cases of PHL it is important to perform a comprehensive review of laboratory data for any subject who meets any of the following identification criteria in isolation or in combination:

- AST  $\geq 3 \times$  ULN
- ALT  $\geq 3 \times$  ULN

CONFIDENTIAL

Study Drug: AC176

Sponsor/Development Innovations Study Number: AC176-001/GU 207

Final Protocol: 10 July 2023 Version 4.0

- $TBL \geq 2 \times ULN$

When a subject meets any of the identification criteria, in isolation or in combination, the central laboratory, if applicable, will immediately send an alert to the Investigator.

Where the identification criteria are met in samples analyzed by a local laboratory, the Investigator will:

- Notify the Sponsor's representative
- Request a repeat of the test (new blood draw) by the local laboratory
- Complete the appropriate unscheduled laboratory case report form (CRF) module(s) and the original laboratory test CRF form

When the identification criteria are met from central or local laboratory results the Investigator will without delay determine whether the subject meets PHL criteria (see "Definitions") by reviewing laboratory reports from all previous visits (including both central and local laboratory results).

The Investigator will without delay review each new laboratory report and if the identification criteria are met will:

- Notify the Sponsor's representative
- Determine whether the subject meets PHL criteria (see "Definitions") by reviewing laboratory reports from all previous visits
- Promptly enter the laboratory data into the laboratory CRF

## **Follow-up**

### Potential Hy's Law criteria not met

If the subject does not meet PHL criteria the Investigator will:

- Inform the Sponsor's representative that the subject has not met PHL criteria
- Perform follow-up on subsequent laboratory results according to the guidance provided in the clinical study protocol

### Potential Hy's Law criteria met

If the subject does meet PHL criteria the Investigator will:

- Determine whether PHL criteria were met at any study visit prior to starting study treatment (see Section 11 Safety Reporting)
- Notify the Sponsor's representative that the subject has met PHL criteria

The Investigator will contact the Medical Monitor to provide guidance, discuss, and agree on an approach for the study subjects' follow-up and the continuous review of data. Subsequent to this contact the Investigator will:

- Monitor the subject until liver biochemistry parameters and appropriate clinical symptoms and signs return to normal or baseline levels, or as long as medically indicated
- Investigate the etiology of the event and perform diagnostic investigations as discussed with the Medical Monitor.
- Complete the liver CRF modules as information becomes available

*CONFIDENTIAL*

Study Drug: AC176

Sponsor/Development Innovations Study Number: AC176-001/GU 207

Final Protocol: 10 July 2023 Version 4.0

- If at any time (in consultation with the Medical Monitor) the PHL case meets serious criteria, report it as an SAE using standard reporting procedures.

### **Review and assessment of potential Hy's Law cases**

The instructions in this section should be followed for all cases where PHL criteria are met.

No later than 3 weeks after the biochemistry abnormality was initially detected, the Investigator will contact the Medical Monitor in order to review available data and agree on whether there is an alternative explanation for meeting PHL criteria other than DILI caused by the investigational product. The Accutar Biotechnology, Inc. Clinical Lead or equivalent and Medical Monitor will also be involved in this review, together with other subject-matter experts as appropriate.

According to the outcome of the review and assessment, the Investigator will follow the instructions below.

If there is an agreed-upon alternative explanation for the ALT or AST and TBL elevations, a determination of whether the alternative explanation is an AE will be made and subsequently whether the AE meets the criteria for a SAE:

- If the alternative explanation is not an AE, record the alternative explanation on the appropriate CRF.
- If the alternative explanation is an AE/SAE, record the AE/SAE in the CRF accordingly and follow the reporting standard practices.

If it is agreed upon that there is no explanation that would explain the ALT or AST and TBL elevations other than the investigational product:

Report an SAE (report term Hy's Law) according to the Sponsor's standard processes.

- The "Medically Important" serious criterion should be used if no other serious criteria apply.
- As there is no alternative explanation for the HL case, a causality assessment of "related" should be assigned.

If there is an unavoidable delay of over 3 weeks in obtaining the information necessary to assess whether or not the case meets the criteria for HL, then it is assumed that there is no alternative explanation until such time as an informed decision can be made:

- Report an SAE (report term Potential Hy's Law) applying serious criteria and causality assessment as per above.
- Continue follow-up and review according to the agreed-upon plan. Once the necessary supplementary information is obtained, repeat the review and assessment to determine whether HL criteria are met. Update the SAE report according to the outcome of the review, amending the reported term if an alternative explanation for the liver biochemistry elevations is determined.

*CONFIDENTIAL*

Study Drug: AC176

Sponsor/Development Innovations Study Number: AC176-001/GU 207

Final Protocol: 10 July 2023 Version 4.0

## **Actions required when potential Hy's Law criteria are met before and after starting study treatment**

This section is applicable to subjects with liver metastases who meet PHL criteria on study treatment having previously met PHL criteria at a study visit prior to starting study treatment.

At the first on-study treatment occurrence of PHL criteria being met, the Investigator will determine if there has been a significant change in the subjects' condition compared with the last visit where PHL criteria were met.

- If there is no significant change, no action is required.
- If there is a significant change, notify the Sponsor's representative.

A "significant" change in the subject's condition refers to a clinically relevant change in any of the individual liver biochemistry parameters (ALT, AST, or TBL) in isolation or in combination, or a clinically relevant change in associated symptoms. The determination of whether there has been a significant change will be at the discretion of the Investigator; this may be in consultation with the Medical Monitor if there is any uncertainty.

## **Actions required for repeat episodes of potential Hy's Law**

This section is applicable when a subject meets PHL criteria on study treatment, and has already met PHL criteria at a previous on-study treatment visit.

The requirement to conduct follow-up, review, and assessment of a repeat occurrence(s) of PHL is based on the nature of the alternative cause identified for the previous occurrence.

The investigator should determine the cause for the previous occurrence of PHL criteria being met and answer the following question:

Was the alternative cause for the previous occurrence of PHL criteria being met found to be the disease under study (e.g., chronic or progressing malignant disease, severe infection, or liver disease), or did the subject meet PHL criteria prior to starting study treatment and at first on-study treatment visit, as described in "Actions required when potential Hy's Law criteria are met before and after starting study treatment".

- If No: Follow the process described in "Potential Hy's Law criteria not met".
- If Yes: Determine if there has been a significant change in the subject's condition compared with when PHL criteria were previously met.

If there is no significant change, no action is required.

If there is a significant change, follow the process described in "Follow-up".

A "significant" change in the subject's condition refers to a clinically relevant change in any of the individual liver biochemistry parameters (ALT, AST, or TBL) in isolation or in combination, or a clinically relevant change in associated symptoms. The determination of whether there has been a significant change will be at the discretion of the Investigator; this may be in consultation with the Medical Monitor if there is any uncertainty.

*CONFIDENTIAL*

Study Drug: AC176

Sponsor/Development Innovations Study Number: AC176-001/GU 207

Final Protocol: 10 July 2023 Version 4.0

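### Appendix F sends some repeat episodes that meet potential Hy's Law criteria to the procedure for cases that do not meet them

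*Protocol*

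**What the plan says.** Appendix F defines PHL as AST or ALT of at least 3 × ULN together with total bilirubin of at least 2 × ULN, at any time after study medication starts. The definition makes no separate provision for repeat episodes.

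The section *Actions required for repeat episodes of potential Hy's Law* opens with its scope: "This section is applicable when a subject meets PHL criteria on study treatment, and has already met PHL criteria" at an earlier on-treatment visit. It then says: "The requirement to conduct follow-up, review, and assessment of a repeat occurrence(s) of PHL is based on the nature of the alternative cause", meaning the cause found at the earlier episode. The Investigator answers one question about that earlier episode: "Was the alternative cause for the previous occurrence of PHL criteria being met found to be the disease under study", or did the patient already meet the criteria before treatment and at the first on-treatment visit? The examples given for disease include severe infection and liver disease.

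- Answer no: "If No: Follow the process described in 'Potential Hy's Law criteria not met".
- Answer yes, with no significant change in condition: no action.
- Answer yes, with a significant change: the *Follow-up* process.

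*Follow-up* has two parts. The part for criteria not met opens "If the subject does not meet PHL criteria the Investigator will", and its first step is "Inform the Sponsor's representative that the subject has not met PHL criteria". Its only other step is to follow later laboratory results as the protocol directs. The part for criteria met includes "Notify the Sponsor's representative that the subject has met PHL criteria", contact with the Medical Monitor, monitoring until recovery, diagnostic investigations agreed with the Medical Monitor, "Complete the liver CRF modules as information becomes available", and SAE reporting if the case becomes serious.

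**The concern.** The instruction and its destination cannot both be right. A patient reaches the repeat-episode section by meeting PHL criteria, and the no answer then sends that patient to a procedure whose opening condition is that the criteria are not met.

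Safety and tolerability are the primary objective of this first-in-human study, and Appendix F is its route for identifying drug-induced liver injury. A site that follows the text would tell the Sponsor's representative that a qualifying case did not qualify, and would have no instruction at that point to involve the Medical Monitor, investigate the cause or complete the liver CRF modules. It could then also fail to start the joint review, due within 3 weeks, and the default rules that go with it. Those rules report an SAE as Hy's Law when no other explanation is agreed, or as potential Hy's Law when the review is unavoidably delayed beyond 3 weeks.

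**Working it through.** No figure is involved, so the check traces the decision path through Appendix F and compares it with the rest of the protocol.

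1. **Entry.** Under *Identification of potential Hy's Law cases*, the Investigator decides afresh, at each triggering laboratory result, whether PHL criteria are met. The repeat-episode section applies only if they are. Everyone inside it therefore meets the criteria now.

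2. **Question.** The question concerns the cause of the previous episode. It does not ask about the current episode and cannot change the fact that the current one meets the criteria.

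3. **Yes branch.** Without a significant change, no action is needed. With one, the patient goes to *Follow-up*. Because the criteria are met, this resolves to the part for criteria met. The branch is coherent.

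4. **No branch.** The patient goes to the part for criteria not met. Its premise contradicts step 1 in every case, and its first step is a report that is untrue. The steps listed for criteria met are bypassed.

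5. **Could a lighter path be intended?** The section does say that the work required for a repeat depends on the earlier cause. That explains taking no action on an unchanged repeat already attributed to disease. It does not explain reporting that criteria were not met when they were.

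6. **Correction elsewhere.** This is current Appendix F text, outside the summary of changes, and no other part of the protocol corrects the cross-reference.

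7. **Who can reach the no branch.** Section 6.2.1 uses the same thresholds (AST/ALT at least 3 × ULN with bilirubin at least 2 × ULN). It requires discontinuation unless a correctable cause unrelated to drug can be documented. To answer no at a repeat, a patient must have stayed in the study after the first episode with a cause that is neither disease nor the pre-treatment pattern. Severe infection and liver disease count as disease in the question. Of the alternative explanations that Appendix F lists in its Hy's Law definition, this leaves mainly another drug, and Section 6.2.1 does not make clear whether a concomitant drug counts as unrelated to drug.

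**The case against.** The strongest reply is that this is one wrong heading in an appendix, rarely reached and well covered by other rules. Much of that stands. The Sponsor's representative is already notified of the triggering laboratory result, and a local result that meets the identification criteria requires a repeat blood draw. Section 6.2.1 still demands a documented non-drug cause or discontinuation. General AE reporting and 24-hour SAE reporting continue. An alert Investigator would see that the opening condition does not fit the patient, and the correct part follows directly under the same *Follow-up* heading. None of this makes the cross-reference right.

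A reader might also infer more than the documents support:

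- **That the repeat episodes least explained by disease are the ones misrouted.** The question is about the previous episode. The cause of the current one has not been assessed in either branch.
- **That the branch is wrong because the review section covers all cases meeting PHL criteria.** The yes branch without change, and the section on patients who met the criteria before treatment, also call for no action. Such a conflict would not be specific to the no branch. The firm ground is the false premise of the destination.
- **That the Cycle 1 DLT rule gives little cover because a second scheduled biochemistry result comes only at Cycle 2 Day 1.** This ignores the mandated repeat draw and the monitoring until recovery, both of which can give further results within Cycle 1.
- **That the size of the problem can be given by counting the steps lost.** Whether each step is covered elsewhere is a matter of judgement, so a count would suggest precision that the text does not give.

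**Conclusion.** The cross-reference is wrong as written. For a patient who meets PHL criteria again on treatment, and whose previous episode was attributed neither to the disease under study nor to the pre-treatment pattern, literal compliance gives a false report and bypasses the steps for criteria met. The review and its default SAE rules are not removed by the text; they may be missed because the site has been told to treat the case as not qualifying.

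The reach is small. The protocol gives no event rate, and the branch depends on a patient staying in the study under Section 6.2.1 with a cause that the repeat-episode question does not class as disease. If another drug does not count as unrelated to drug under that section, the branch may be close to empty. No endpoint, sample size or analysis is affected. The case for correction rests on the error being plain, on its place in the liver-safety procedure of a first-in-human study, and on how easily it is put right.

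**What to change.** In the repeat-episode section of Appendix F, change the destination of the no answer to *Potential Hy's Law criteria met*, followed by *Review and assessment of potential Hy's Law cases*. The yes branch needs no change for this point. Make the correction at the next amendment and send sites a short notice. The cost is one cross-reference and that notice, with no change to visits, endpoints or sample size.

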## Appendix G: PK Sampling Timepoint Schedules

**Table 8 PK Sampling Timepoints Once Daily (QD Dosing)**

	Timepoints relative to AC176 dosing*	ECG* (in triplicate)
Cycle 1 Day 1	Pre-dose	X
	1 hour ( $\pm 5$ minutes)	-
	2 hour ( $\pm 5$ minutes)	-
	3 hour ( $\pm 10$ minutes)	-
	4 hour ( $\pm 10$ minutes)	X
	6 hour ( $\pm 20$ minutes)	-
	8 hour ( $\pm 1$ hour)	X (if feasible)
	10 hour ( $\pm 1$ hour)	-
	12 hour ( $\pm 1$ hour)	-
	24 hour ( $\pm 1$ hour)	-
Cycle 1 Day 15	Pre-dose	X
	1 hour ( $\pm 5$ minutes)	-
	2 hour ( $\pm 5$ minutes)	-
	3 hour ( $\pm 10$ minutes)	-
	4 hour ( $\pm 10$ minutes)	X
	6 hour ( $\pm 20$ minutes)	-
	8 hour ( $\pm 1$ hour)	X (if feasible)
	10 hour ( $\pm 1$ hour)	-
	12 hour ( $\pm 1$ hour)	-
	24 hour ( $\pm 1$ hour)	-
Cycle 2 Day 1	Pre-dose**	X**
Cycle 4 Day 1	Pre-dose**	X
Cycle 6 Day 1	Pre-dose**	X

\* Depending on emerging PK data, the SRC may alter the timepoints for PKs and ECGs. \*\* For the Expansion cohort, this timepoint is needed to be collected, the rest of the time points are not needed. With Sponsor approval the required 10 hour and 12 hour PK sample collections may be omitted, if not feasible.

Meal consumption prior to PK collections will be collected. The last meal consumed prior to dosing on the day of full 24 hour PK collections (Cycle 1) should be recorded.

Additional unscheduled PK samples may be drawn during the study if it is deemed clinically indicated for the patient and/or based on newly emerged data from clinical studies of AC176. Similarly, if any PK timepoint is later deemed unnecessary per acquired clinical PK data, such timepoint may be removed from the PK schedule.

*CONFIDENTIAL*

Study Drug: AC176  
Final Protocol: 10 July 2023 Version 4.0

Sponsor/Development Innovations Study Number: AC176-001/GU 207

Table 9 PK Sampling Timepoints – Intermittent Dosing 7 days On / 7 days Off (28 days per cycle)

	Timepoints relative to AC176 dosing*	ECG* (in triplicate)
Cycle 1 Day 1	Pre-dose	X
	1 hour(±5 minutes)	-
	2 hour(±5 minutes)	X
	3 hour(±10 minutes)	-
	4 hour(±10 minutes)	-
	6 hour(±20 minutes)	-
	8 hour(±1 hour)	X (if feasible)
	10 hour(±1 hour)	-
	12 hour(±1 hour)	-
	24 hour(±1 hour)	-
Cycle 1 Day 8	Pre-dose	X
	1 hour(±5 minutes)	-
	2 hour(±5 minutes)	-
	3 hour(±10 minutes)	-
	4 hour(±10 minutes)	X
	6 hour(±20 minutes)	-
	8 hour(±1 hour)	X (if feasible)
	10 hour(±1 hour)	-
	12 hour(±1 hour)	-
	24 hour(±1 hour)	-
Cycle 2 Day 8	Pre-dose**	X**
Cycle 4 Day 8	Pre-dose**	X
Cycle 6 Day 8	Pre-dose**	X

\* 7 days on and 7 days off, e.g., C1D1 to C1D7 receive AC176. Dose interrupted C1D8 to C1D14. AC176 dose to continue Cycle 1 on C1D15 to C1D21 and interrupted C1D22 to C1D28. From Cycle 2, the patients will be dosed for 7 days and interrupted 7 days. \*\* For the Expansion cohort, this timepoint is needed to be collected, the rest of the time points are not needed. With Sponsor approval the required 10 hour and 12 hour PK sample collections may be omitted, if not feasible. Meal consumption prior to PK collection will be collected. The last meal consumed prior to dosing on the day of full 24 hour PK collections (Cycle 1) should be recorded. If the sample cannot be collected at the visit as scheduled, it should be collected at the next visit whenever possible.

CONFIDENTIAL

Study Drug: AC176

Sponsor/Development Innovations Study Number: AC176-001/GU 207

Final Protocol: 10 July 2023 Version 4.0

